2.12 Rationale for leukapheresis

To assess the expansion of rare precursor B-cell populations that occur at a frequency of approximately 1 out of 20 million cells, a large number of peripheral blood mononuclear cells (PBMCs) is required. Leukapheresis can provide 6 to 10 billion PBMCs without depleting red blood cells or other blood components. There are approximately 1 million PBMCs per milliliter of blood; therefore, peripheral blood sampling at volumes associated with typical blood donation (~500 mL) would not provide sufficient PBMC numbers. Furthermore, leukapheresis is associated with fewer AEs when compared to blood donation. Hence, this protocol will employ leukapheresis in all study participants to ensure adequate specimens for analysis of rare precursors. Leukapheresis will be performed at screening and after the third dose of sD-NP-GT8 has been administered. The rationale for performing leukapheresis at 2 weeks after the third dose is based on previous studies that have assessed potentially rare VRC01-class memory B cells in the periphery (49).

Leukapheresis is a safe and well tolerated procedure with several studies reporting no significant late effects attributable to the procedure (50, 51). The protocol team has developed eligibility requirements for the proposed procedures (see Section 5.1) and leukapheresis eligibility criteria (see Section 8.6) as well as accounting for guidelines from the American Society for Apheresis, the American Society of Hematology, and review of the scientific literature.

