The team has also considered whether to include temporal limits on platelets/INR, and a temporal requirement to abstain from NSAID/aspirin use prior to leukapheresis and has decided not to include these as restrictions (48). We note that the trial eligibility criteria exclude persons with bleeding disorders (eg, factor deficiency, coagulopathy, or platelet disorder requiring special precautions (see Section 5.1.2). Assessment of patients post leukapheresis found the most frequent side effect (39%) was paresthesia due to citrate-related hypocalcemia, managed with oral calcium supplements and/or slower rates. No bleeding occurred (52). The study team conclude that adverse reactions with leukapheresis are similar to those reported for conventional PBMC collections. Routine measurement of INR has demonstrated no ability to identify patients who are at risk of periprocedural bleeding even with higher risk procedures such as placement of central venous catheter (47).

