Guidance for participants scheduling licensed vaccines or allergy treatments: In order to prevent interference with reactogenicity assessments, participants who plan to receive licensed vaccines or allergy treatments should be counseled to avoid scheduling receipt of these substances, when possible, within the 2 week interval after study product administration. To avoid unnecessary delays in study product administration, participants should be counseled to avoid scheduling receipt of these substances before study product administration (see Section 5.2.1).

Symptom diaries: Participants are asked to record symptoms on a daily basis using an electronic participant diary (paper alternative is available). All participants will be given a thermometer for oral temperature measurement and a ruler, and will be provided access to the electronic diary (paper alternative available). All participants will be provided training on diary completion, proper thermometer usage, and how to use of the measuring device to measure any injection-site induration and/or erythema. Participants will use the diary to record daily their highest temperature as well as local and systemic signs and symptoms. For Groups 1 and 2, symptoms are recorded for the day of vaccination and for 7 full days following each vaccination. For Group 3 only, symptoms are recorded for the day of vaccination, for 7 full days following the first two vaccinations, and for 14 full days following the third and fourth vaccinations. Participant diaries will be reviewed by a clinician and reconciled for accuracy and completeness. Attribution assessment will be performed and recorded on a case report form (CRF) for systemic reactogenicity events reported in the participant diary after additional evaluation of the participant by clinician. Clinicians may photograph the injection site in order to document injection-site reactogenicity.

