- ⁴ Contraception status assessment is required only for participants who were assigned female sex at birth and are capable of becoming pregnant. Participants will also be provided with counselling about contraception.
- ⁵ Risk-reduction counseling per CRS Standard Operating Procedures (SOP).
- ⁶ Concomitant medications, including prescription and nonprescription drugs, vitamins, topical products, alternative/complementary medicines, recreational drugs, vaccinations, and allergy shots, are recorded during screening, at enrollment, and at each subsequent clinic visit.
- ⁷ During concomitant medications check-in participant is counseled to avoid medications that would increase the risk of bleeding for 7 days prior to FNA (see Section 8.5).
- ⁸ Vaccination (in-clinic assessments): At least 60 minutes after the first vaccination and after the fourth vaccination, and 30 minutes after for all other vaccinations. Prior to clinic discharge, the injection site and systemic symptoms will be assessed, and participants will have vital signs taken.
- 9 Reactogenicity: Clinic staff will follow new or unresolved reactogenicity symptoms present at the final reactogenicity day (see Section 8.3 and HVTN 305 SSP)
- 10 Pregnancy test: For participants assigned female sex at birth. Pregnancy test may be performed on blood specimens. Persons who are NOT capable of becoming pregnant due to total hysterectomy or bilateral oophorectomy (verified by medical records) or menopause (no menses for ≥ 1 year) are not required to undergo pregnancy testing. For persons who are confirmed pregnant, pregnancy testing is not required unless clinically indicated.
- ¹¹ Local labs may assign appropriate alternative tube types for locally performed tests.
- ¹² HIV screening test: See Section 5.1.1.
- ¹³ **Research samples:** Blood-draw volumes for each tube type shown. Alternate tube types may be used under certain conditions (eg, product shortages) upon approval of the HVTN Laboratory Center. Refer to the Specimen Collection SSP for more information.
- ¹⁴ Blood draw will be performed before vaccination.
- ¹⁵ **Leukapheresis:** May be performed prior to enrollment visit once the participant has been found to have met all protocol enrollment criteria (see Section 5.1.1 and 5.1.2) and leukapheresis eligibility criteria (see Section 8.6).
- ¹⁶ Fine Needle Aspiration: Target for FNA is 3 weeks post–second and –third vaccinations.

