Appendix C Visit windows

Visit #	Visit Type	Lower allowable window (-)	Lower target window (-)	Target day*	Upper target window (+)	Upper allowable window (+)up
01	Screening Leukapheresis	-56	-	0	-	+0
02	Enrollment / Vaccination 1	-	-	1	-	-
03	2 weeks postvaccination 1	-	-4	15	+4	+7
04	Vaccination 2	-	-	29	+9	+28
05	2 weeks postvaccination 2	-	-4	43	+4	+7
06*	FNA postvaccination 2	-	-4	50	+4	+10
07	Vaccination 3	-	-	85	+14	+28
08	2 weeks postvaccination 3 Leukapheresis Primary immunogenicity	-	-4	99	+4	+7
09*	FNA postvaccination 3	-	-4	106	+4	+10
10	Vaccination 4 (Group 3 only)	-	-7	169	+14	+28
11	2 weeks postvaccination 4 for Group 3; follow-up visit for Groups 1 and 2	-	-4	183	+4	+7
12	Final clinic visit	-28	-14	365	+14	+28
AESI**	AESI contact	-21	-14	547	+14	+28

All target dates are relative to Day 1, with the exception of visits, 3, 5, 8, and 11 (for Group 3 only) which are relative to the vaccination immediately preceding the visit.

^{*}Visits 06 and 09 are only applicable to participants providing lymph node FNA collections. The FNA visits are relative to the preceding vaccination.

^{**}This contact must be at least 12 months post last vaccination

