9.2 Safety Analyses

Reactogenicity: The number and percentage of subjects experiencing each type of reactogenicity sign or symptom will be tabulated by severity. For a given sign or symptom, each subject's reactogenicity will be counted once under the maximum severity for all assessments.

Adverse Events: AEs will be coded into Medical Dictionary for Regulatory Activities (MedDRA) preferred terms. The number and percentage of subjects experiencing each specific AE will be tabulated by severity and relationship to study vaccine. For the calculations in these tables, each subject's AE will be counted once under the maximum severity or strongest recorded causal relationship to treatment. A complete listing of AEs for each subject will provide details including severity, relationship to treatment, onset, duration and outcome.

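### The Visit 8 leukapheresis can fall inside Group 3's dose-3 symptom diary but never inside that of Groups 1 and 2, and the reactogenicity analysis has no rule for symptoms that start after it

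*Protocol*

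**What the plan says.** **Diary length (Protocol 8.3).** "For Groups 1 and 2, symptoms are recorded for the day of vaccination and for 7 full days following each vaccination". Group 3 has the same 7-day period after its first two doses, but records symptoms "for 14 full days following the third and fourth vaccinations".

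**Timing of the procedure (Protocol Appendix C).** Visit 8 is listed as "2 weeks postvaccination 3 Leukapheresis Primary immunogenicity", with target Day 99, a target window of 4 days either side and an upper allowable limit of +7. Target dates count from the first vaccination, "with the exception of visits, 3, 5, 8, and 11 (for Group 3 only) which are relative to the vaccination immediately preceding the visit". I read the parenthesis as belonging to Visit 11, since only Group 3 has a fourth dose. Visit 8 therefore moves with the actual date of the third dose in every group.

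**Who has it (Protocol 2.12).** "this protocol will employ leukapheresis in all study participants", at screening and after the third DNA dose.

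**End of the diary (Protocol Appendix A, footnote 9; same text in Appendix B).** "Clinic staff will follow new or unresolved reactogenicity symptoms present at the final reactogenicity day".

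**Analysis (SAP 9.2; Protocol 6.4.3 is equivalent).** For a given symptom, "each subject's reactogenicity will be counted once under the maximum severity for all assessments". Section 8.3 has a clinician record attribution for systemic diary events. Neither analysis section says that this attribution is used, and neither mentions symptoms that begin after a study procedure.

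**The concern.** Reactogenicity is primary endpoint 1a. Groups 2 and 3 receive the same DNA regimen and differ by the adjuvanted Trimer, so readers will set their reactogenicity columns side by side even though no formal safety comparison is planned.

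Every participant has leukapheresis about two weeks after dose 3, but only Group 3 may still be completing a diary on that day. Because the tabulation takes the worst grade, a single post-procedure entry can set a participant's recorded severity. Any such misclassification runs one way: it can raise Group 3's rate and cannot raise the others'. Footnote 9 sharpens this, because staff are told to follow symptoms that are new on the final diary day, and in Group 3 that is the target day of the procedure.

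**Working it through.** **Inputs.** Vaccination 3 on Day 85 (Protocol 1.5, Table 1-1). Visit 8 target Day 99, target window -4/+4, upper allowable +7, no lower allowable limit given (Appendix C). Diary of vaccination day plus 7 days (Groups 1 and 2) or plus 14 days (Group 3, doses 3 and 4) (Section 8.3). Group 3 size 18.

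**1. The plan's own figure.** 85 + 14 = Day 99, which matches Appendix C.

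**2. Visit 8 window.** 99 - 4 = Day 95; 99 + 4 = Day 103; 99 + 7 = Day 106. That is 9 target-window days, and 12 days from Day 95 to the allowable limit.

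**3. Diary after dose 3.** Groups 1 and 2: Day 85 to 85 + 7 = Day 92. Group 3: Day 85 to 85 + 14 = Day 99.

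**4. Overlap.**

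| | Groups 1 and 2 | Group 3 |
|---|---|---|
| Target day inside diary | no | yes (last day) |
| Target-window days inside | 0 of 9 | 5 of 9 (Days 95-99) |
| Days 95-106 inside | 0 of 12 | 5 of 12 |

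The earliest in-window Visit 8 is 95 - 92 = 3 days after the Groups 1 and 2 diary closes. A late third dose does not change this, because diary and visit both move with it.

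**5. What is not affected.** Days 85-92 precede any in-window leukapheresis in all groups. Appendices A and B schedule leukapheresis only at Visits 1 and 8, so the dose-4 diary (Day 169 to 169 + 14 = Day 183) contains none. The post-dose-3 lymph node aspiration is no earlier than 106 - 4 = Day 102, after Group 3's diary ends.

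**6. Could the procedure produce a solicited symptom?** The solicited systemic items in Section 8.3 are raised temperature, fatigue, myalgia, arthralgia, headache, chills and nausea; the local items concern the injection site. For leukapheresis, Section 2.13.1 names hypocalcemia, pain, bruising, rare infection and fainting, and says further risks depend on local procedure. Section 2.12 reports that "the most frequent side effect (39%) was paresthesia due to citrate-related hypocalcemia". Paresthesia is not a diary item. Pain would count only if recorded at the injection site or as generalized muscle or joint pain.

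**7. Size.** One participant of 18 is 1/18 = 5.6 percentage points. For one symptom, added rate in Group 3 = (1 - p) x q x f, where p is the share who already have it at that grade from vaccination, q the chance that leukapheresis causes it, and f the share of procedures done by Day 99. The formula treats these as independent. **The documents supply neither p nor q; all values here are assumptions.** With p = 40%:

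| q | f = 1 (all by Day 99) | f = 5/9 | f = 5/12 |
|---|---|---|---|
| 0% | 0 | 0 | 0 |
| 5% | 3.0 points | 1.7 | 1.3 |
| 10% | 6.0 points | 3.3 | 2.5 |
| 20% | 12.0 points | 6.7 | 5.0 |

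At q = 10% this is 18 x 0.060 = 1.1, 18 x 0.033 = 0.6 or 18 x 0.025 = 0.45 participants. The extreme of p = 20%, q = 20%, f = 1 gives 0.8 x 0.2 = 16 points. The fractions 5/9 and 5/12 assume visits spread evenly over the window. If the table takes the maximum over all doses, p accumulates over four doses and the added rate shrinks. Groups 1 and 2 gain 0 in every cell under the Section 8.3 diary.

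**The case against.** The strongest reply is that the causal link is thin. The documents attribute no solicited systemic symptom to leukapheresis, describe it as well tolerated and say it causes fewer adverse events than blood donation. A reader might take the 39% paresthesia figure as a measure of the bias; it is not, because paresthesia is not solicited. This stands, and it is why no size can be claimed.

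A reader might also infer that Group 2 against Group 3 is the only view of what the Trimer adds, and that this view is spoiled. That does not hold. Dose 4 gives Trimer without DNA, with a 14-day diary and no leukapheresis, and Days 85-92 compare the groups cleanly. Safety is tabulated descriptively and set against historical controls, so no test is invalidated.

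The asymmetry is not independent of the unequal diary lengths; it follows from them. Endpoint 1a (Protocol 3.1, SAP 3.1) describes collection for at least two weeks after any vaccine, which conflicts with the 7-day period in Section 8.3. Under that wording all groups would reach Day 99 and the asymmetry would vanish, although procedure symptoms could then enter every group's table.

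There are partial safeguards. Section 8.3 defines reactogenicity as signs considered to come from the vaccine, clinicians reconcile diaries, and attribution is recorded for systemic events. The SAP does not state that procedure-attributed symptoms are counted; it is silent. But silence leaves the choice to whoever programs the table, and local events carry no attribution under that section. Footnote 9 itself concerns follow-up and does not create the overlap; Section 8.3, Appendix C and SAP 9.2 do.

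Finally, any bias overstates risk, and cutting the main table off at the procedure could remove real late reactions. Both points are fair, and they argue for adding a tabulation rather than truncating one.

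**Conclusion.** The point holds as a gap in the analysis rules. Under Section 8.3 and Appendix C, leukapheresis can fall within Group 3's dose-3 diary (5 of 9 target-window days, 5 of 12 to the allowable limit) and cannot fall within that of Groups 1 and 2. Nothing in Protocol 6.4.3 or SAP 9.2 keeps a procedure-caused solicited symptom out of Group 3's reactogenicity rate.

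The direction is known and the size is not. It may be near zero and is probably modest; at this group size a single participant is visible. A visit on Day 100 or later does not overlap, and one on Day 99 leaves only the rest of that day in the diary.

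The documents do not support saying that Group 3's reactogenicity will be materially inflated, or that the Trimer's tolerability cannot be judged. The conclusion rests on the Section 8.3 diary periods governing over the endpoint 1a wording.

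**What to change.** In SAP 9.2 and Protocol 6.4.3, keep the full-period reactogenicity table and add:

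- **(a)** a tabulation of all groups over the shared period of vaccination day plus 7 days, for reading between groups;
- **(b)** for Group 3 after dose 3, a separate row for solicited symptoms with onset or worsening on or after the date of leukapheresis, shown with the attribution already recorded for systemic events. Treat the procedure day as post-procedure.

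Reconcile the collection period in endpoint 1a (Protocol 3.1 and SAP 3.1) with Section 8.3. If the reconciled text has all groups reporting through Day 99, row (b) should cover all groups.

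**Cost.** One or two extra descriptive rows, built from diary dates, the leukapheresis date and attribution the study already records. No visit moves and no entry leaves the main table. The SAP is already due for update before the first Safety Monitoring Board report and before the final analysis. The limitation is that daily entries cannot split the procedure day into before and after, so some vaccine symptoms on that day will appear in row (b) as well as in the main table.

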Appendix B Schedule of procedures: Participants not undergoing FNA

Visit	Number	01	02	03	04	05	06	07	08	09	10	11	12	AESI ¹⁶
	dy Week		0	2	4	6	7	12	14	15	24	26	52	78
	ly Month		0	0.5	1	1.5	1.75	3	3.5	3.75	6	6.5	12	18
S	tudy Day	-56 to 0	1	15	29	43	50	85	99	106	169	183	365	547
P	rocedure	Screen ¹	Vac 1		Vac 2			Vac 3			Vac 415			
Study procedures														
Assessment of Understanding		V												
Informed consent		V												
Medical history ²		V												
Physical exam ³		V	√	√	√	√		√	√		√	√	√	
Contraception status assessment ⁴		V	√		√			√			√			
Social impact assessment			√	√	√	√		√	√		√	√		
Social impact questionnaire					√			√					$\sqrt{}$	
Risk-reduction counseling ⁵		V	√	√	√	√		√	√		√	√	√	
Concomitant medications ⁶		V	√	√	√	√		√	√		√	√	√	
Adverse Events (AEs)			√	√	√	√		√	√		√	√		
AESIs/MAAEs/SAEs			√	√	√	√		√	√		√	√	√	V
Vaccination ⁷			√		√			√			√			
Reactogenicity assessment ⁸			√		√			√			√			
EP injection site assessment				√	√	√		√	√		√	√	$\sqrt{}$	$\sqrt{16}$
Clinical labs	Tube													
Pregnancy test (urine or serum) 9,10		V	√		√			√	√		√			
HBsAg/anti-HCV ¹⁰	SST	5												
HIV screening test, 10,11	SST	5												
Calcium ¹¹	SST	5												
CBC/Differential ¹⁰	EDTA	5		5		5			5			5		
ALT & Creatinine ¹⁰	SST	5		5		5			5			5		
HIV diagnostic test	EDTA							10				10	20	
Research samples ¹²														
PBMC for assays & storage	ACD			42.5		136		136 ¹³				136	178.5	
Serum for assays and storage	SST	34		34		34			34			34	34	
Leukapheresis ¹⁴		V							V					
Daily vol	ume (mL)	59	0	86.5	0	180		146	44		0	190	232.5	
56-day total vol	ume (mL)			145.5	145.5	325.5		326	370		0	190	232.5	

Green shading: Vaccination visit for all groups; Blue shading: Vaccination visit for Group 3 only; Gray shading: FNA visit not applicable to this subgroup.

- ¹ Screening evaluations at Visit 01 are performed no more than 56 days before Day 1.
- ² Medical history: A complete medical history is performed during screening. At enrollment and at subsequent visits, an interim medical history may be performed.
- ³ A complete **physical exam** is performed at screening and last clinic visit to include height, weight, and vital signs, and clinical assessments of head, ears, eyes, nose, and throat; neck and lymph nodes; heart; chest; abdomen; extremities; neurological function; and skin. At other visits, a **targeted physical exam** will be performed as needed, based on participant reports or indications of illness.
- ⁴ Contraception status assessment is required only for participants who were assigned female sex at birth and are capable of becoming pregnant. Participants will also be provided with counselling about contraception.
- ⁵ Risk-reduction counseling per CRS Standard Operating Procedures (SOP).
- ⁶ Concomitant medications, including prescription and nonprescription drugs, vitamins, topical products, alternative/complementary medicines, recreational drugs, vaccinations, and allergy shots, are recorded during screening, at enrollment, and at each subsequent clinic visit.
- ⁷ Vaccination (in-clinic assessments): At least 60 minutes after the first vaccination and after the fourth vaccination, and 30 minutes after for all other vaccinations. Prior to clinic discharge, the injection site and systemic symptoms will be assessed and participants will have vital signs taken.
- ⁸ Reactogenicity: Clinic staff will follow new or unresolved reactogenicity symptoms present at the final reactogenicity Day (see Section 8.3 and HVTN 305 SSP)
- ⁹ Pregnancy test: For participants assigned female sex at birth. Pregnancy test may be performed on blood specimens. Persons who are NOT capable of becoming pregnant due to total hysterectomy or bilateral oophorectomy (verified by medical records) or menopause (no menses for ≥ 1 year) are not required to undergo pregnancy testing. For persons who are confirmed pregnant, pregnancy testing is not required unless clinically indicated.
- ¹⁰ Local labs may assign appropriate alternative tube types for locally performed tests.
- ¹¹ HIV screening test: See Section 5.1.1.
- ¹² Research samples: Blood-draw volumes for each tube type shown. Alternate tube types may be used under certain conditions (eg, product shortages) upon approval of the HVTN Laboratory Center. Refer to the Specimen Collection SSP for more information.
- ¹³ Blood draw will be performed before vaccination.
- ¹⁴ Leukapheresis: May be performed prior to enrollment visit once the participant has been found to have met all protocol enrollment criteria (see Section 5.1.1 and 5.1.2) and leukapheresis eligibility criteria (see Section 8.6).
- ¹⁵ Vaccination 4/Visit 10 will be conducted only for participants assigned to Group 3.
- ¹⁶ **AESI contact:** CRS staff will contact study participants at month 18 to collect the information listed in Section 8.10. The EP-injection–site assessment will be an abbreviated questionnaire that can be conducted over the phone.

Appendix C Visit windows

Visit #	Visit Type	Lower allowable window (-)	Lower target window (-)	Target day*	Upper target window (+)	Upper allowable window (+)up
01	Screening Leukapheresis	-56	-	0	-	+0
02	Enrollment / Vaccination 1	-	-	1	-	-
03	2 weeks postvaccination 1	-	-4	15	+4	+7
04	Vaccination 2	-	-	29	+9	+28
05	2 weeks postvaccination 2	-	-4	43	+4	+7
06*	FNA postvaccination 2	-	-4	50	+4	+10
07	Vaccination 3	-	-	85	+14	+28
08	2 weeks postvaccination 3 Leukapheresis Primary immunogenicity	-	-4	99	+4	+7
09*	FNA postvaccination 3	-	-4	106	+4	+10
10	Vaccination 4 (Group 3 only)	-	-7	169	+14	+28
11	2 weeks postvaccination 4 for Group 3; follow-up visit for Groups 1 and 2	-	-4	183	+4	+7
12	Final clinic visit	-28	-14	365	+14	+28
AESI**	AESI contact	-21	-14	547	+14	+28

All target dates are relative to Day 1, with the exception of visits, 3, 5, 8, and 11 (for Group 3 only) which are relative to the vaccination immediately preceding the visit.

^{*}Visits 06 and 09 are only applicable to participants providing lymph node FNA collections. The FNA visits are relative to the preceding vaccination.

^{**}This contact must be at least 12 months post last vaccination

